3.5.5.2 Program delivery

The *PREHAB CR* program will be delivered by a multi-disciplinary group consisting of physicians, nurses, fitness professionals, physiotherapists, dieticians, and psychologists. This approach allows the *CR* team to share knowledge, skills, and patient care responsibilities. A medical advisor, at each site, is responsible for the safety of enrolled *PREHAB* patients. Additionally to support patient safety, an emergency plan is in place with appropriate equipment (e.g. Defibrillator, nitroglycerine) and medical staff is available during patient care hours.

3.5.5.3 Core Components of Cardiac Rehabilitation

The *PREHAB CR* program adheres to the core components of *CR* outlined by the Canadian Association for Cardiac Rehabilitation Guidelines (85). These core components include: systematic patient referral processes, patient assessments, health behavior interventions and risk factor modification, exercise training, leisure time activities, outcomes assessment programs, continuous quality improvement programs, and continuous professional development programs.

3.5.5.4 Patient assessment

All patients complete a series of assessments that are kept in a client case file. All patient health information collected and will be is kept in a secure room and a lockable filing cabinet. Patient health information is used to assist the *CR* health care team to optimize patient treatment during the *CR* program.

3.5.5.4.1 Risk factor assessment

Patients who are enrolled in *PREHAB* will complete a one hour patient assessment from nurse or fitness professional. This assessment includes a medical history and physical examination to collect information on cardiac risk factors or other underlying conditions that could affect their treatment. Furthermore, each center collects blood samples for information on patient cholesterol, fasting blood glucose, and hemoglobin. In most cases, patients have received screening and diagnostic procedures from the

“The PREHAB Study” (Pre-operative Rehabilitation for reduction of Hospitalization After coronary Bypass and valvular surgery.)

hospital in which their cardiac event was acutely managed. This information serves as a decision-making tool for *CR* staff to make informed decisions on patient treatment during *CR*. The information collected from this patient assessment is used to stratify a patient’s risk for experiencing a future cardiac event.

3.5.5.4.2 Exercise stress test and 6-minute walk test (6MWT)

All *PREHAB* patients complete a graded maximal exercise stress test (*GXT*), which is supervised by an MD, exercise specialist, nurse, and electrocardiogram technician. Patients complete the Modified Bruce treadmill protocol. This protocol was designed specifically for testing patient cardiac function during exercise. Briefly, each stage of the test lasts three minutes, where speed and grade is increased at each stage. The first stage starts at 1.7 miles per hour and a 10% grade for the first three minutes and is progressively increased thereafter by increasing both speed and grade. There are a total of seven stages. The test is terminated if the patient voluntarily withdraws, or if the *CR* staff notices any cardiac abnormalities during the test (e.g., ST-abnormalities, no increase in heart rate with an increase in workload). Information collected from the stress test is then used to assist *CR* staff to prescribe exercise for the patient. A *6MWT* will be performed in all patients along with the *GXT* as described in the methodology.

3.5.5.4.3 Psychosocial assessment

The research literature supports the contention that depression and anxiety negatively affect the cardiovascular health status of patients. Therefore, patients are encouraged, particularly if they had a previous psychosocial disorder, to see a clinical psychologist for an initial assessment. This assessment is used to counsel the patient on ways in which they can appropriately manage their cardiac disease in combination with their psychosocial disorder. Patients also complete the 5 item Geriatric Depression Scale (*GDS-5*).

3.5.5.4.4 Nutritional assessment

PREHAB patients will see the Registered Dietician at the *CR* Centre to optimize their diet to help manage their disease. Prior to the assessment, patients complete a 3-day food recall to help the Dietician in developing a personalized message and treatment strategy. Furthermore, this assessment assists patients in gaining a better understanding of the ways in which different types of fats, salt intake, as well as other components of the diet affect cardiovascular health. Patients also have the option to receive a follow-up visit to receive further counseling.

3.5.5.5 Health behavior interventions and risk factor modification

PREHAB patients all receive a comprehensive, multi-faceted health behavior intervention with the goal of positively modifying their risk factor profile. This includes nutritional counseling, lipid management, hypertension management, smoking cessation, weight management, diabetes management, adherence to prescribed pharmacotherapy, psychosocial management, and physical activity counseling.

3.5.5.6 Exercise training and leisure time activities

After the baseline assessments described above are completed, the *PREHAB* patient will engage in the 8-week *PREHAB CR* exercise therapy program. The first four weeks of the program constitutes a more structured program, the *CR* Centre staff closely monitor the patient during their exercise program and follows their progress. The patient attends the *CR* Centre for two 1 hour sessions of exercise training for the first four weeks. Exercise intensity is typically prescribed at 85% of their maximum heart rate-reserve, unless advised otherwise by the Internist. The remaining 4 weeks is less-structured and the patient is given more autonomy on the manner in which they complete their exercise therapy program. The patient engages in an individually prescribed exercise program consisting of aerobic, strength, and flexibility training. Frequency, time, and type of exercise varies depending on what the patient chooses. The majority of aerobic exercises consist of walking, cycling, rowing, and many machine-based aerobic

“The PREHAB Study” (Pre-operative Rehabilitation for reduction of Hospitalization After coronary Bypass and valvular surgery.)

exercises. A Strength and Stretch class is also offered to increase muscle strength and endurance, and flexibility.

In addition to participating in physical activity at the *CR* Centre, patients are encouraged to participate in physical activities during their leisure time. This includes, but is not limited to, walking outdoors, gardening, household chores, grocery shopping, and cycling. This component of the *CR* program is designed to help patients manage their cardiac disease after they complete *CR*. Patients will be assigned an accelerometer to wear to be able to compare self-assessed exercise reporting with objective measurements.

3.5.5.7 Outcomes assessment

Patients are evaluated after they complete the *CR* program based on their outcomes. Patients are assessed based on several different outcomes, including clinical, health, educational, and behavioral outcomes. To assess these outcomes, patients complete the baseline assessments (described under the Patient assessment section) after they complete the 8-week *PREHAB CR* program. A key evaluation will be the *6MWT* to assess exercise capacity pre and post-program.

3.5.5.8 Continuous quality improvement programs

Each *CR* program will engage in continuous evaluation of their program to provide high quality care for their patients. The key components of this evaluation include:

- Eliminating defects in the *CR* delivery process and adding features to better meet the needs of the patient needs and preferences.
- Focusing on the core processes to improve the *CR* program. This includes statistical methods and tools to identify desired performance levels, measurement of current performance, and to interpret and take action as necessary.
- Involvement of all *CR* staff in quality improvement. Utilization of structured teams and councils to advise and plan quality improvement strategies are utilized.
- Setting high standards for performance.

3.5.5.9 Continuous professional development programs

This process involves keeping up to date with the most relevant knowledge on delivering the appropriate care to patients. Continuous professional development includes:

- Continuous learning processes that update relevant knowledge, skills, and attitudes.
- Maintenance of professional continuing education credits.
- Keeping up to date on the appropriate certifications (e.g., CPR training)
- Staff engagement in employee mentorship of students and other professionals, professional certification programs, and attendance in annual meetings relevant to *CR*.

3.5.6 Variable Waitlist Time

We acknowledge that the time on the waiting list may be variable. For example, in Manitoba the median waitlist time is 12 weeks (range: 3-31 weeks). The median waitlist time for our preliminary study was 62 days and such we believe that enrolled patients will not be subjected to any undue harm. The recommended standard wait for elective cardiovascular surgery should not exceed six weeks,(86) however the best physiological outcomes for patients attending cardiac rehabilitation is at least eight weeks(21)(19)(20)(79), or occur by participants who attend more than 25 sessions of *CR*.(11) After consulting with the associated *CR* program sites and our expert co-investigators, it was determined that the preferred *Prehab* intervention would be 8 weeks because it was deemed that clinically stable, frail, elderly patients could feasibly achieve measurable health benefits and risk factor modification over this

“The PREHAB Study” (Pre-operative Rehabilitation for reduction of Hospitalization After coronary Bypass and valvular surgery.)

time frame.(87) However due to the variability in the waitlist times participants would still be eligible with a waitlist time of 4 weeks minimum.

What if patients are unable to complete the Prehab program due to a change in surgical date?

It is possible that a patient may not complete the full 8 week program due to scheduling changes for their procedure. We and others (78)(11)have seen functional and health behavior improvements in as little as 2-4 weeks. Notably, 2 patients in our pilot *Prehab* project participated in the program for only 3.5 weeks but still improved their total distance walked by an average of 174 meters (43% improvement). Our data is supported by Fiorina and associates and indicates that as few as 15 days of *CR* can improve total distance walked by as much as 40%. With this in mind, the *Prehab* program has been structured to provide the more intensive nutritional counselling, educational, psychosocial and exercise therapy during the first four weeks of the program and engage *Prehab* participants to take control of their self-managed care for the remaining program. This will enable participants to gain meaningful benefits in the event scheduling changes prevent the completion of the 8 week program.

3.5.6 Qualitative review of PREHAB Study

We engaged patients prior to conducting the PREHAB study to uncover whether patients would participate in a prehabilitation intervention. After study completion we want to continue the conversation with all patients both in the intervention arm, standard care arm as well as registry participants.

During the post study intervention we will conduct a series of individual interviews and survey components to enlist patient-centered response and opinion to the study intervention. We wish to know if there were barriers for participation, any factors that reduced adherence to the study as well as an overall satisfaction with the intervention. We also would like to discuss how improvements can be made after a participant has finished the intervention part of the study. For non-intervention patients we want to see if they went to cardiac rehab post-surgery and what its impact was on their recovery.

Additionally, A small group of participants and their caregivers from the primary site will be contacted and asked to participate in a more extensive patient panel session to better understand the patient valued experience of the intervention that was provided to participants and ways to improve delivery and adherence. We will conduct 3 group sessions of patients and their caregivers lasting approximately 2-3 hours. We will be following a general format with topic questions; however, we expect a very open conversation. All information will be transcribed and stored. Information identified within these sessions may be used to develop tool to be used to improve communication and adherence to care based interventions during the perioperative process. (See PREHAB Patient panel protocol)

We will conduct interviews with patients based on availability. As we are a multi-site intervention we will interview patients from the study who are not local to the primary site. We will contact current participants and enroll patients who are interested in the study. We will also identify patient perspective with cardiac rehabilitation post-surgery .

3.6 Data collection

All participants will meet with the research staff at nine time points: 1) twice at time of enrolment after their acceptance for a surgical procedure (i.e. baseline pre-intervention); 2) 4 weeks following randomization into either standard care or intervention group; 3) twice, 1-week

“The PREHAB Study” (Pre-operative Rehabilitation for reduction of Hospitalization After coronary Bypass and valvular surgery.)

preoperatively (i.e. Pre-op); 4) twice, 3 months postoperatively; and, 5) twice, 1 year postoperatively (Figs. 4 and 5). Data collection will occur from both written and electronic medical records sources (i.e. patient information systems, where applicable). Existing perioperative surgical, *ICU* and hospital data will be used to capture patient demographics, procedure urgency, intraoperative procedure and anesthetic variables, cardiopulmonary bypass information, blood product utilization, mechanical ventilation, delirium/coma, *ICU* and hospital *LOS*, major adverse events, infection and *ICU* and hospital recidivism are collected in institutional databases.

Patients deemed “unsafe” to be enrolled in the exercise portion of the study or that have refused to be randomized but have consented to participate in the follow up registry will be contacted via telephone by research staff after their surgeries at two time points: 1) 3-months after surgery; and, 2) 12-months after surgery. A data sharing agreement, in compliance with provincial patient confidentiality legislation will be created to permit planned analysis. We have previously utilized these data collection methods.(49)(65)(88)(89)(90)

4 Safety Monitoring

Safety data including new hospitalization, worsening angina or heart failure and arrhythmias will be captured and all adverse events will be reportable to the study Data Safety Monitoring Board (*DSMB*). The *DSMB* is an independent group of experts that advises study investigators. They are responsible to periodically evaluate the study data for participant safety and study conduct, in addition to making recommendations concerning the modification and/or termination of the trial.

Safety Monitoring: Clinical stability during the pre-habilitation period is to be evaluated twice per week by the *CR* team using clinical questioning in comparison to their baseline stress test. All cases will be reviewed in conjunction with the attending physician.

5 Statistical Analysis Plan

5.1 Measures/Outcomes:

For the *PREHAB* study, we propose to capture data to enable evaluation of effect of a preoperative cardiac pre-habilitation program on:

5.1.1 Primary Outcome

Proportion of patients with hospital length of stay >7 days.

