2.4 The PREHAB Study – Primary Research Questions/Hypotheses

The primary research question(s) for the *Prehab* study include:

- i. What is the effect of a preoperative cardiac pre-habilitation (“*Prehab*”) program on the proportion of patients with hospital length of stay (*LOS*) > 7 days.
We hypothesize that the performance of a multifaceted, interdisciplinary cardiac “*Prehab*” program in patients awaiting an elective cardiac surgery will reduce the proportion of frail elderly patients requiring a postoperative hospital *LOS* > 7 days.
- ii. What is the effect of a preoperative cardiac pre-habilitation program in high-risk frail elderly patients on (1) pre-operative frailty, (2) exercise capacity, (3) self-managed physical activity behavior, (4) in-hospital outcomes, (5) 3-month clinical outcomes, and (6) 3 month health-related quality of life.
We hypothesize that the “*Prehab*” program for frail elderly patients awaiting an elective cardiac surgery will reduce frailty, improve exercise capacity, improve self-managed physical activity behavior, improve in-hospital outcomes, improve clinical outcomes 3 months and 1 year postoperatively, and improve health-related quality of life.

3 Study Design

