3.4.3 In-Hospital Outcomes

Postoperative *ICU* and hospital *LOS*, 30-day mortality, major adverse events (death, *MI*, stroke or renal failure requiring dialysis) will be collected using existing site surgical databases. Post-operative *CR* enrollment will be assessed using administrative data from the participating *CR* centers.

In our preliminary analysis, we have identified a strong association between frailty and the occurrence of delirium (Table 5). The participating Cardiac *ICUs* currently perform an agitation and delirium assessment once every 8 hours as standard practice. Delirium assessment will be performed in the *ICU* using the Richmond Agitation-Sedation Scale (*RASS*)(59) and the Confusion Assessment Method for the Intensive Care Unit (*CAM-ICU*). (60)(61)(62). As part of standard of care a blood sample will be collected upon placement of the arterial line in the operating room to ascertain the patient’s sodium, potassium, glucose, white blood cell count, hematocrit, creatinine and albumin and this data will also be collected.(49)(65)

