5.2 Statistical/Analytical Plan

Objective 1: To determine if *Prehab* reduces the proportion of frail elderly patients requiring a prolonged hospital length of stay of >7 days. A univariable analysis will be undertaken to determine if hospital *LOS* > 7 days is associated with frailty and other patient-level factors. A stepwise multivariable logistic regression model will then be developed to determine if *Prehab* attendance is independently associated with a decreased risk of prolonged hospital length of stay > 7 days. As a secondary analysis, hospital *LOS* will also be compared as a continuous variable between the *Prehab* and standard care groups using a Mann-Whitney test.

“The PREHAB Study” (Pre-operative Rehabilitation for reduction of Hospitalization After coronary Bypass and valvular surgery.)

Objective 2: Does attending *Prehab* influence frailty, exercise capacity, physical activity behavior, in-hospital complications, and *HRQoL*? Although we will employ four different measures of frailty, based on our preliminary data and based on a Task Force’s position statement(90), the Modified Fried Criteria will be the primary frailty outcome over time from baseline to the end of *Prehab* program (pre-operatively), or from baseline to the 3-month post-operative follow-up. The primary measure of exercise capacity will be the *6MWT* and will be analysed with univariable linear regression models to evaluate the association between the *6MWT* and *Prehab* attendance. Accelerometers will be used to objectively measure the number of minutes spent performing moderate to vigorous physical activity (*MVPA*) and total physical activity (*TPA*) per day for a period of 7 days and compared between groups. A composite outcome for a major adverse cardiac event (i.e. *MACCE* = in-hospital stroke, myocardial infarction, renal failure requiring dialysis and death) and delirium will be compared between groups using a Chi-Square or Fisher’s Exact test. A multivariable logistic regression will be used to identify if *Prehab* is independently associated with in-hospital delirium. The *SF-12v2* and *EQ-5D* scores, after normative standardization, will be analyzed through use of a repeated *ANOVA* to allow for a standardized group and group/time interaction effect estimation.

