5.3 Sample Size Calculation

The sample size calculation was based on the primary objective – determining the effect of *Prehab* on rates of prolonged hospital length of stay > 7 days. Our preliminary data, demonstrated the proportion of frail patients in the Control group with a hospital length of stay > 7 days to be 58.3%. For the *Prehab* group, based on improvements in functional capacity in our pilot *RCT* and the work by Arthur et al14, we believe an absolute 20% reduction in proportion of patients that require prolonged hospital length of stay of greater than 7 days, is feasible. A sample size of 194 individuals (97 in each group) will be required for a two-tailed test at an alpha of 0.05 and power of 80%. All patients assigned to the pilot *Prehab* group completed the intervention, however, we are mindful that we will be recruiting frail, elderly patients who may have a higher dropout rate. Hence, we are estimating a 20% dropout rate and plan to recruit 244 individuals (122 in each study arm) to achieve an eventual sample size of 194 after dropout.

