6.3 Data quality assurance

Data entered by each site will be password-protected and the ability to access or change data prior to locking of the database will be restricted to the project manager. Once initial data collection has been completed, missing data and implausible values will be identified using predetermined objective criteria, and queries resolved through direct communication with sites if required. This data cleaning process will be overseen by the *PREHAB* management committee. Treatment of outliers and missing data will be in accordance with the statistical analysis plan.

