Albumin (g/L)	39.0 (3.1)	36.4 (4.5)	0.0011
Chronic renal failure	0 (0.0%)	4 (5.6%)	0.1245
Creatinine (μmol/L)	90 (76 – 100)	85 (71 – 116)	0.8231
GI disease	14 (23.0%)	27 (37.5%)	0.0702
PVD	4 (6.6%)	13 (18.1%)	0.0478
Dyslipidemia	40 (65.6%)	51 (70.8%)	0.5155
Pulmonary hypertension	2 (3.3%)	4 (5.6%)	0.6870
Hypertension	48 (78.7%)	65 (90.3%)	0.0624
CHF	30 (49.2%)	40 (55.6%)	0.4631
MI	20 (32.8%)	31 (43.1%)	0.2249
Atrial fibrillation	7 (11.5%)	15 (20.8%)	0.1478
Prior angioplasty or stent	5 (8.2%)	18 (25.0%)	0.0107
Prior cardiac surgery	4 (6.6%)	2 (2.8%)	0.4124
Visual impairment	17 (27.9%)	19 (26.4%)	0.8482
Hearing impairment	3 (4.9%)	5 (6.9%)	0.7260
EuroSCORE II (%)	1.42 (0.87 – 1.94)	2.02 (1.25 – 4.28)	0.0001
Self-health rating (0-4)	3 (2 – 3)	2 (1 – 2)	<0.0001
MoCA score (0-30)	26 (24 – 27)	22 (20 – 25)	<0.0001

“The PREHAB Study” (Pre-operative Rehabilitation for reduction of Hospitalization After coronary Bypass and valvular surgery.)

Table 5 - Intraoperative Variables

Intra-Operative Characteristics	Not Frail (n=61)	Frail (n=72)	P-Value	OR (95% CI)
Procedure type			0.5729	
- Isolated CABG	26 (42.6%)	39 (54.2%)		
- Isolated Valve	19 (31.2%)	17 (23.6%)		
- CABG + Valve	12 (16.7%)	13 (18.1%)		
- Other	4 (6.6%)	3 (4.2%)		
CPB time (minutes)	102 (80 – 132)	89 (68 – 121)	0.1712	

Table 6 - Unadjusted Association of Frailty and Risk of Negative Postoperative Outcome

Post-Operative Outcomes	Not Frail (n=61)	Frail (n=72)	P-Value	OR (95% CI)
ICU LOS (days)	2 (1 – 3)	2 (1 – 3)	0.2819	
Hospital LOS (days)	6 (5 – 9)	8 (6 – 12)	0.0098	
ICU LOS > 72 hours	10 (16.4%)	17 (23.6%)	0.3025	1.58 (0.66 – 3.76)
Hospital LOS > 7 days	23 (37.7%)	42 (58.3%)	0.0177	2.31 (1.15 – 4.65)
Major adverse event	1 (1.6%)	4 (5.6%)	0.3742	3.52 (0.38 – 32.45)
Post-operative Delirium	4 (6.6%)	20 (27.8%)	0.0015	5.48 (1.76 – 17.09)
In-hospital mortality	0 (0.0%)	2 (2.8%)	0.4997	undefined
Discharge to Institution	1 (1.6%)	4 (5.6%)	0.3713	3.64 (0.40 – 33.45)

Categorical variables are listed as frequency values (%), continuous variables are listed as mean (standard deviation) or median (interquartile range). Statistical comparisons were calculated using Chi-Square or Fisher Exact Test for categorical variables, T-Test or Mann-Whitney Test for continuous variables.

Table 7 - Comparison of baseline data between Standard care and Prehab groups

	Standard care (n= 7)	Prehab (n= 7)	P-value
Demographics			
Age (years)	63 ± 3	64 ± 4	0.63
Gender (% female per group)	1 (14%)	2 (25%)	0.99

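### The primary endpoint has no rule for in-hospital death; read literally, a death by day 7 counts as a favourable short stay

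*Combined protocol and SAP*

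**What the plan says.** The primary outcome in section 5.1.1, repeated in the synopsis, is "Proportion of patients with hospital length of stay >7 days". The hypothesis in section 2.4 is that the programme "will reduce the proportion of frail elderly patients requiring a postoperative hospital *LOS* > 7 days". Section 5.2 analyses the binary outcome by stepwise logistic regression and adds that "hospital *LOS* will also be compared as a continuous variable between the *Prehab* and standard care groups using a Mann-Whitney test".

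None of these places mentions death. Death appears elsewhere:

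- Section 3.4.3 collects "Postoperative *ICU* and hospital *LOS*, 30-day mortality, major adverse events (death, *MI*, stroke or renal failure requiring dialysis").
- Section 5.2 tests "A composite outcome for a major adverse cardiac event (i.e. *MACCE* = in-hospital stroke, myocardial infarction, renal failure requiring dialysis and death") between groups as a secondary outcome.
- Section 4 sends adverse events to the DSMB.

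Three other passages might have supplied a rule and do not. The daily readiness-for-discharge check in section 3.4.1 deals with non-medical delay. The intention-to-treat statement in section 3.2 says who is analysed, not how a death is scored. Section 6.3 says "Treatment of outliers and missing data will be in accordance with the statistical analysis plan", but section 5, which is that plan, has no missing-data rule.

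**The concern.** A patient who dies on day 3 has a stay of 3 days. Under the endpoint as written, that patient has not stayed more than 7 days and counts as a good outcome. In the Mann-Whitney test the same patient ranks among the shortest stays. This is the opposite of what the hypothesis means by not requiring a long stay.

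The literal reading is not the only one. An analyst could also exclude the patient, treat LOS as missing, or count the death as a failure. The text does not choose between them.

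At stake is the case where early mortality differs between arms. The literal rule then misses that harm in the primary endpoint, or partly turns it into apparent benefit when some of the patients who died would otherwise have stayed beyond 7 days. In an open-label trial, a choice between rules that can give different answers should be made before the data are seen.

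**Working it through.** **The plan's own figure.** Section 5.3 takes "the proportion of frail patients in the Control group with a hospital length of stay > 7 days to be 58.3" per cent (42/72 in Table 6), an absolute reduction of 20 points, two-sided alpha 0.05 and 80% power. The pooled-variance formula for 58.3% against 38.3% gives 96.8, so 97 per group. With 20% dropout, 97/0.8 = 121.25, so 122 per arm. The stated sample size reproduces.

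**How many deaths to expect.** Table 6 ("Unadjusted Association of Frailty and Risk of Negative Postoperative Outcome") gives in-hospital mortality of 2/72 = 2.8% in frail patients, exact 95% CI 0.3% to 9.7%. Per arm of 122: 122 × 2/72 = 3.4 deaths on any day. The day of death is not given, so the share falling by day 7 is unknown.

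**Shift from three excess early deaths in an arm of 122.** Let p be the arm's rate of LOS over 7 days, and assume these three patients would otherwise have exceeded 7 days at that rate.

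| Rule | Formula | p = 38.3% | p = 58.3% |
|---|---|---|---|
| Literal (non-event) | −3p/122 | −0.9 points | −1.4 points |
| Excluded | (122p − 3p)/119 − p | 0 | 0 |
| Failure | +3(1 − p)/122 | +1.5 points | +1.0 points |

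If all three would have stayed beyond 7 days, the literal shift reaches its maximum of 3/122 = 2.5 points. The gap between the literal and failure rules is 3/122 = 2.5 points (3/97 = 3.1 at 97 per group) whatever their stay would have been.

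**How large an imbalance this is.** If a fraction f of the 3.39 expected deaths falls by day 7 (assumption), three more is a rise of (3.39f + 3)/(3.39f): 1.9-fold at f = 1, 2.8-fold at f = 0.5 and 4.5-fold at f = 0.25.

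**Effect on the test.** Illustration at 97 per group with control 57/97, three early deaths in Prehab and none in control; uncorrected chi-square, unadjusted (the planned model is logistic).

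| Prehab patients over 7 days | Literal | Excluded | Failure |
|---|---|---|---|
| 43 | 43/97, p = 0.044 | 43/94, p = 0.072 | 46/97, p = 0.114 |
| 37 (near the planned effect) | 37/97, p = 0.004 | 37/94, p = 0.007 | 40/97, p = 0.015 |

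**Ranking.** In Table 6 the frail median LOS is 8 days (IQR 6 to 12), and 72 − 42 = 30 of 72 (41.7%) stayed 7 days or less. A death by day 7 therefore ranks below the median, and one in the first days falls below the lower quartile.

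**Sample size with death in the event.** As an upper bound, let both cohort deaths be early and not already counted: (42 + 2)/72 = 61.1%. Against 41.1% the same formula gives 96.9, so still 97 per group.

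**The case against.** The strongest case against is that this is small.

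- **The example is selected.** With control 57/97 and a 3–0 split of early deaths, the literal and failure rules differ in significance only at 41, 42 or 43 Prehab events. In simulations at the planned rates with equal early mortality of 0.7%, 1.4% or 2.8%, the three rules disagreed in about 3%, 5% and 8% of trials. A 3–0 split arose in only about 1% to 3%. With no LOS effect, each rule fixed in advance kept type I error near 5%. This stands, and it limits the weight of the point. If early mortality doubles in Prehab (1.4% against 2.8%), however, disagreement is about 8%, mostly with the literal rule significant and the failure rule not.
- **The mortality base may be too high.** It comes from patients frail by the Modified Fried criteria, whereas the trial enrols at Clinical Frailty Score 3 or more. The whole preliminary cohort had 2/133 = 1.5%, or 1.8 deaths per 122. That is a fair lower figure, although the frail subgroup is the one the plan itself uses for its control rate.
- **Exclusion is unlikely.** The trial is intention to treat, and Table 6 uses the denominator 72 for both LOS and mortality. This narrows the choice but does not show whether a death counts as a long stay.
- **Mortality is examined elsewhere.** The composite and the DSMB may detect harm. The primary result could still credit the same deaths as benefit.
- **A composite changes the question.** This is a real cost, met by reporting LOS over 7 days alone as a supportive analysis.

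**Conclusion.** The concern holds. No section says how an in-hospital death enters the primary endpoint or the LOS comparison, and the literal reading scores a death by day 7 in the wrong direction. The sample size is not in error.

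The size is modest: negligible if early mortality is balanced, and 2.5 points between the literal and failure rules for three excess early deaths in an arm of 122. That can decide a borderline result but does not overturn a clear 20-point effect. The estimate rests on a mortality rate from two deaths, on an unknown share of deaths by day 7, and, for the shifts within each rule, on those patients having the arm's average chance of a long stay. The plan should be changed because the event is foreseeable and the remedy is cheap.

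**What to change.** In section 5.1.1 and the synopsis, define the primary event as postoperative hospital LOS over 7 days or in-hospital death, taking the postoperative qualifier from section 2.4. In section 5.2, use the same event in the logistic model and give in-hospital deaths the worst rank in the Mann-Whitney test. Report LOS over 7 days without the death component as a prespecified supportive analysis.

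The cost is wording in three places. LOS and death are already collected under section 3.4.3, and 97 per group still suffices if early mortality is equal and the 20-point difference is kept. The downside is that the primary becomes a composite and is slightly less purely a measure of bed use.

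Randomised patients who never have surgery have no postoperative LOS; they need a separate rule, which this change does not supply.
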